## 1.6 For Investigational Use Only

The MGC Health COVID-19 & Flu A+B Home Multi Test is a lateral flow immunochromatographic antibody assay intended for the simultaneous qualitative detection and differentiation of the nucleocapsid antigen from SARS-CoV-2, influenza A and/or influenza B directly from anterior nasal swab specimens obtained from individuals, who are suspected of respiratory viral infection within five (5) days of symptom onset. This test is intended for nonprescription home use with self-collected direct anterior nares swab samples from individuals ages 14 years and older or adult lay user collected anterior nares swab samples from individuals aged 2 to 13 years. The performance characteristics of the test using nasal swabs have not been established. The results obtained from this study will not be used for diagnostic purposes or patient management.

Results are intended for the simultaneous identification of SARS-CoV-2, influenza A, and/or influenza B, which are generally detectable in nasal samples during the acute phase of infection. Positive results indicate the presence of viral antigens, but clinical correlation with patient history and other diagnostic information is necessary to determine infection status. Positive results do not rule out bacterial infection or co-infection with other viruses. The agent detected may not be the definite cause of disease.

## 1.7 Study Sites

Study enrollment for this study will be conducted at one (1) testing site in the US. The site will attempt to enroll a diverse demographic patient population with varying educational backgrounds.

The applicable Institutional Review Board (IRB) will review and approve the study protocol, informed consent and assent, Quick Reference Instructions (QRI), and subject questionnaire and test illustrations prior to enrolling subjects into this study.

#### 1.8 Study Objectives

The objective of this protocol is to determine the usability of the MGC Health COVID-19 & Flu A+B Home Multi Test in a simulated home use environment.

#### 1.9 Study Design

This is an open label observational study to evaluate the usability of the MGC Health COVID-19 & Flu A+B Home Multi Test.

Each subject will be provided a MGC Health COVID-19 & Flu A+B Home Multi Test and asked to conduct the test on themselves or another subject using the Quick Reference Instructions (QRI) for the MGC Health COVID-19 & Flu A+B Home Multi Test while being monitored by an observer.

A member of the clinical study staff will observe the subject while they are conducting the test. The observer will note the completion and/or correct performance of critical steps which, if not performed correctly, could lead to an inaccurate test result.

The observer will note whether or not they agree with the subject's interpretation of the test results. A photograph of the test cartridge will be taken showing the results.

Subjects will be asked to provide their perspective on the use of the test at the end of the testing process.

In addition, a set of illustrations of test results will be provided to each subject for interpretation. Results of the testing will be used to determine whether further refinement of the QRI may be needed. The results of the testing will not be used for patient management or treatment decisions.

# 2 STUDY ENROLLMENT AND WITHDRAWAL

## 2.1 Study Population

Enrollment must include 15 subjects ages 14 and older, and 15 subjects ages 2-13 who present to the office location for COVID-19 and/or flu testing. The intent is to enroll subjects with varying educational levels and socioeconomic backgrounds.

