# **Study Synopsis**

Title	MGC Health COVID-19 & Flu A+B Home Multi Test Usability Study
Protocol Number	MGC-1001
Protocol Date	16 January 2023
Protocol Version	1.0
Study Sponsor	Medical Group Care
Study Purpose	The purpose of this study is to evaluate the usability of the MGC Health COVID-19 & Flu A+B Home Multi Test in home use.
Investigational Material/Product	The MGC Health COVID-19 & Flu A+B Home Multi Test is a lateral flow immunochromatographic antibody assay intended for the simultaneous qualitative detection and differentiation of the nucleocapsid antigen from SARS-CoV-2, influenza A and/or influenza B directly from anterior nasal swab specimens obtained from individuals, who are suspected of respiratory viral infection within five (5) days of symptom onset. This test is intended for non-prescription home use with self- collected direct anterior nares swab samples from individuals ages 14 years and older or adult lay user collected anterior nares swab samples from individuals aged 2 to 13 years.
Study Objective	The objective of the study is to determine the usability of the MGC Health COVID-19 & Flu A+B Home Multi Test in a simulated home use environment.
Study Design	This is an open label study to evaluate the usability of the MGC Health COVID-19 & Flu A+B Home Multi Test using information from the Quick Reference Instructions (QRI).
Inclusion Criteria	
 
Subjects are eligible for inclusion if the following criteria are met:         
 
An Institutional Review Board (IRB) approved informed consent / assent, if applicable, is signed and dated prior to any study related activities.
 
Male and female subjects 2 years of age and older.
 
Subject is willing to provide a self-collected nasal swab sample. (If the subject is under the age of 14, an adult lay user will collect the sample.)
 
Subject agrees to complete all aspects of the study.
 
 
 

Exclusion Criteria	
 
A subject is not eligible for inclusion if any of the following criteria apply:
 
1. Subject has a visual impairment that cannot be restored with glasses or contact lenses.
 
2. Subject has prior medical or laboratory training.
 
3. Subject uses home diagnostics, e.g., glucose meters, HIV tests.
 
4. Subject has prior knowledge of their current COVID-19 or flu infection status.
 

Target	A minimum of 30 completed subjects with a minimum of 15 subjects	

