Population /	testing themselves and a minimum of 15 subjects testing another person	
Sample Size	(child 2 to 13 years old).	
Site	1 testing site in the United States	
Requirements		
Study Duration	The overall study duration is expected to be less than one (1) month, with	
Study Duration	subject participation completed in one visit of approximately one hour.	
	Primary Endpoints	
	1. Assess the usability of the Quick Reference Instructions (QRI)	
Study Endpoints	based upon observer evaluation.	
	2. Assess the usability of the kit for home use based upon subject	
	evaluation.	

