#### 1.5.1 Intended Use

The MGC Health COVID-19 & Flu A+B Home Multi Test is a lateral flow immunochromatographic antibody assay intended for the simultaneous qualitative detection and differentiation of the nucleocapsid antigen from SARS-CoV-2, influenza A and/or influenza B directly from anterior nasal swab specimens obtained from individuals, who are suspected of respiratory viral infection within five (5) days of symptom onset. This test is intended for nonprescription home use with self-collected direct anterior nares swab samples from individuals ages 14 years and older or adult lay user collected anterior nares swab samples from individuals aged 2 to 13 years.

Results are for the simultaneous identification of SARS-CoV-2, influenza A, and influenza B. The MGC Health COVID-19 & Flu A+B Home Multi Test is not intended to detect influenza C antigens. These viral antigens are generally detectable in anterior nasal swab specimens during the acute phase of infection. Positive results indicate the presence of viral antigens, but clinical correlation with patient history and other diagnostic information is necessary to determine infection status. Positive results do not rule out bacterial infection or co-infection with other viruses. The agent detected may not be the definite cause of disease. Individuals who test positive with the MGC Health COVID-19 & Flu A+B Home Multi Test should self- isolate and seek follow-up care with their physician or healthcare provider as additional testing may be necessary.

Negative SARS-CoV-2 results should be treated as presumptive and confirmed with a molecular assay, if necessary, for patient management. Negative results do not rule out SARS-CoV-2 infection and should not be used as the sole basis for treatment or patient management decisions, including infection control decisions. Negative results should be considered in the context of an individual's recent exposures, history, and the presence of clinical signs and symptoms consistent with COVID-19.

Negative influenza A and B test results should be treated as presumptive. It is recommended these results be confirmed by viral culture or an FDA cleared influenza A and B molecular assay. Negative results do not preclude influenza virus infection and should not be used as the sole basis for treatment or other management decisions.

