#### 3.4 Baseline Data

The site will provide a narrative describing how the testing simulated a home environment. For example, whether a table and chair were provided, how subjects could sanitize their hands, positioning of the subject such that they could not observe others conducting the test, and position of the observer.

Upon confirmation of eligibility to participate in the study, the following information will be obtained:

- Age (For subjects under 14 years of age, the age of the person collecting and testing the sample will also be recorded.)
- Sex
- Race
- Ethnicity
- Educational Level (For subjects under 14 years of age, the educational level of the person performing the test will be recorded.)

- Occupation (For subjects under 14 years of age, the occupation of the person performing the test will be recorded.)
- Exposure to someone with COVID-19, and the number of days prior to the visit the exposure occurred.
- Presence or absence of respiratory symptoms: fever or chills; cough; shortness of breath; difficulty breathing; muscle or body aches, new loss of taste or smell. Subjects will be asked the date each symptom appeared.
- COVID-19 vaccine status and number of doses, manufacturer, and date of last vaccine.
- Flu vaccine status and date of vaccine, if applicable.

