# 7.1 Usability Study and Risk Mitigation for User Errors

The results will be analyzed to confirm the proper use of the QRI and usability of the MGC Health COVID-19 & Flu A+B Home Multi Test. The usability of the MGC Health COVID-19 & Flu A+B Home Multi Test will be considered valid if:

- The mean score of the subjects' response scores in the questionnaire are  $\leq 3$  for those questions with a score response between 1 and 5.
- 80% of the critical steps were performed correctly based upon the observer's assessment.
- 80% of the interpretation of the sample image results were correct.

The subject questionnaires and observer notes will be used to modify the QRI, if necessary, and additional usability testing will be conducted if needed.

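### The child quota covers ages 2-13 with no minimum for the youngest, so the claim from age 2 could rest on few or no children aged about 2-5

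*Combined protocol and SAP*

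**What the plan says.** Section 1.5.1 claims use with "adult lay user collected anterior nares swab samples from individuals aged 2 to 13 years". The synopsis sets the sample as "A minimum of 30 completed subjects with a minimum of 15 subjects" "testing themselves and a minimum of 15 subjects testing another person", the other person being a child of 2 to 13. Section 2.1 repeats this as "Enrollment must include 15 subjects ages 14 and older, and 15 subjects ages 2-13", drawn from people who come to the office for COVID-19 or flu testing. Inclusion criterion 2 asks only for age 2 or older. No section divides the 2-13 band.

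Two statements touch on the mix of participants. Section 2.1 adds: "The intent is to enroll subjects with varying educational levels and socioeconomic backgrounds". Section 1.7 adds: "The site will attempt to enroll a diverse demographic patient population with varying educational backgrounds". Both are aims rather than requirements, and neither mentions the age of the children.

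Under 7.1, usability is valid if the mean questionnaire score is at most 3, if "80% of the critical steps were performed correctly based upon the observer's assessment", and if 80% of image readings are correct. None of the three depends on the child's age or is applied separately to the adults testing a child.

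Section 3.4 records the subject's age and, for subjects under 14, "the age of the person collecting and testing the sample will also be recorded". The quoted words concern the tester. The child's own age comes from the general age item in the same list.

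**The concern.** The first critical step in 3.5 is to swab each nostril with at least 5 rotations against the nostril. Of the eight steps, it depends most directly on the child's cooperation. It is reasonable to expect it to be harder with a child of 2 to 5 than with one of 12, although the documents give no data on this. The quota treats the two as interchangeable, and fifteen children aged 10-13 would satisfy every enrolment rule.

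Some rules could also tilt the sample towards older children. Inclusion criteria 3 and 4 ask for willingness to provide a sample and to complete the study, 2.4 allows withdrawal for non-compliance, and the synopsis counts completed subjects. A child who resists the swab could be replaced by an older one, although difficulty with such a child is something a usability study should observe.

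At stake is whether the conclusion for the lower part of the claimed age range rests on observation.

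**Working it through.** **The plan's own figure.** 15 self-testers + 15 testing a child = 30, which matches the stated minimum. There is no power calculation to reproduce.

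**How many young children might be seen.** Let s be the share of enrolled children aged 2-5. The documents do not give s, so the values below are assumptions. The highest, 4/12 = 33%, is the share if ages are uniform over the 12 years from 2 to 13. With n = 15 and independent enrolment:

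- P(none) = (1 − s)^15
- P(at most 2) = (1 − s)^15 + 15·s·(1 − s)^14 + 105·s²·(1 − s)^13

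| s (assumed) | Expected number (15 × s) | P(none) | P(at most 2) |
|---|---|---|---|
| 10% | 1.5 | 20.6% | 81.6% |
| 20% | 3.0 | 3.5% | 39.8% |
| 33% | 5.0 | 0.2% | 7.9% |

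**What a small number can show.** Suppose a use error affects 30% of adults swabbing a young child (assumption). The chance of seeing it at least once is 1 − 0.7² = 51% with two such children and 1 − 0.7⁵ = 83% with five.

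**Whether the 80% rule would expose a swabbing problem.** Section 3.5 lists 8 critical steps. Suppose all 15 adults testing a child fail the swabbing step and every other step in the study is done correctly.

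- Child group: 15 × 8 = 120 steps, 15 wrong, 105/120 = 87.5%.
- All subjects: 30 × 8 = 240 steps, 15 wrong, 225/240 = 93.8%.
- Each affected subject alone: 7/8 = 87.5%.

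All three exceed 80%. Section 7.1 does not say over what unit the 80% is counted. If it were applied to each step separately over all 30 subjects, this extreme case would fail (15/30 = 50%). Swabbing failures with six young children and no others would still reach 24/30 = 80%.

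**Room in the pooled rule.** 80% of 240 is 192, so 48 errors are allowed. With perfect self-testers (120 of 120), the child group could have only 192 − 120 = 72 of 120 steps correct, or 60%, and the criterion would be met.

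**The case against.** The strongest reply is that the extreme case is unlikely. Eligibility starts at age 2, and apart from the possible tilt from the willingness and withdrawal rules, nothing steers enrolment towards older children. With uniform ages, the chance of no child aged 2-5 is 0.2%. This stands: the realistic shortfall is one or two young children rather than none, and even that depends on the assumed share.

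A reader might also infer that enrolling older children could turn a fail into a pass. Take 90% of steps correct with an older child and 50% with a child aged 2-5. The child group then scores (13 × 0.9 + 2 × 0.5)/15 = 84.7% with two young children and (10 × 0.9 + 5 × 0.5)/15 = 76.7% with five. The documents do not support this inference, for two reasons. First, 7.1 sets no criterion for the child group alone; pooled with 15 self-testers at 90%, the results are (28 × 0.9 + 2 × 0.5)/30 = 87.3% and (25 × 0.9 + 5 × 0.5)/30 = 83.3%, both passes. Second, 50% over all eight steps does not follow from difficulty with one. With swabbing at 50% and the other seven steps at 90%, a young child's test averages (0.5 + 7 × 0.9)/8 = 85.0%.

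It can also be said that the 2-5 band and the number five appear nowhere in the documents, that age is already recorded, and that 7.1 provides for revised instructions and further testing if needed. The first is correct, so both are offered as examples. The other two lessen the consequence, but a problem that was never observed cannot prompt a revision.

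**Conclusion.** The point holds as a gap in coverage. A study run exactly to plan could support the claim from age 2 with few children near that age, and nothing in 1.7, 2.1 or 7.1 prevents it. The size is uncertain because the age mix is unknown: the chance of at most two children aged 2-5 runs from 8% to 82% over assumed shares of 33% down to 10%. These figures assume independent enrolment at a constant share.

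The 80% rule is no safeguard, because a failure confined to swabbing leaves the step rate above 80% when steps are counted together. For the same reason a quota alone would hardly move the criterion; the swabbing step has to be reported on its own.

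The documents do not show that young children will probably be absent, or that the pass/fail result would change. This is an inexpensive improvement, not an obstacle to running the study.

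**What to change.** In 2.1 and the synopsis, set a minimum number of young children within the existing 15, for example about 5 aged 2-5, which is roughly the uniform share (15 × 4/12 = 5). The exact number and band are for the sponsor to choose and justify.

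In 7.1, add a descriptive report, by child age band (for example 2-5 and 6-13), of the swabbing step on its own and of the overall critical-step rate. The subject's age recorded under 3.4 is sufficient, so no new data item is needed.

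The total stays at 30. Recruitment must be steered and may take slightly longer, and the observed step rate may fall. With five children each one moves the result by 1/5 = 20 percentage points, so the subgroup figures can describe but not test.

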# 2.2 Enrollment Criteria

Subjects are eligible for enrollment only if all of the inclusion criteria are met and none of the exclusion criteria apply.

#### 2.2.1 Inclusion Criteria

- 1. An Institutional Review Board (IRB) approved informed consent / assent, if applicable, is signed and dated prior to any study-related activities.
- 2. Males and females ages 2 and older.
- 3. Subject is willing to provide a self-collected nasal swab sample. (If the subject is under the age of 14, an adult lay-user will collect the sample.)
- 4. Subject agrees to complete all aspects of the study.

#### 2.2.2 Exclusion Criteria

- 1. Subject has a visual impairment that cannot be restored with glasses or contact lenses.
- 2. Subject has prior medical or laboratory training.
- 3. Subject uses home diagnostics, e.g., glucose meters, HIV tests.
- 4. Subject has prior knowledge of their current COVID-19 or flu infection status.

#### 2.3 Study Duration

The overall study duration is expected to be less than one (1) month, with subject participation completed in one visit of approximately one hour.

## 2.4 Subject Withdrawal

Subjects may discontinue their participation in the study at any time. A subject may be withdrawn from the study at any time at the discretion of the investigator.

A subject may be considered withdrawn for the purpose of this study if:

- The subject or parent / legal guardian of the subject withdraws consent for study participation
- The subject is non-compliant with study procedures
- The investigator determines to withdraw the subject if study participation is no longer in the subject's best interest.

# **3 STUDY PROCEDURES**

# 3.1 Set Up

Testing will take place in a room to simulate the home environment. A table with chairs will be available. The observer will stand or sit to the side of the subject providing enough space to: 1) ensure there is no interference with the subject's activities and 2) allow adequate view of the subject's interaction with the test kit. Other than providing the test kit and QRI, the observer will not provide any other directions on how to use the kit.

Each box of the MGC Health COVID-19 & Flu A+B Home Multi Test contains one (1) each of the following: sterile nasal swab, test cassette, and the sample collection tube with nozzle lid. Upon completion of the testing, the used test components will be disposed of properly per local regulations.

At the conclusion of testing and the subject's completion of the questionnaire, the observer will present ten (10) images of different test results and ask the subject to interpret each test result.

#### 3.2 Informed Consent

Study staff trained in basic human research subjects protection will explain the study protocol, procedures, and objectives to the subject and obtain written informed consent and assent, if applicable, for participation in the study from each subject prior to performing any study procedures. The study staff will review all information in the consent / assent, if applicable, allowing subjects ample time to review the form(s), ask questions and have their questions answered to the satisfaction of the subject. Subjects willing to participate will sign the consent / assent, if applicable, and will be provided a copy for their records.

#### 3.2.1 Vulnerable Populations

The study will be conducted in accordance with the relevant articles of the Declaration of Helsinki. The Declaration of Helsinki defines vulnerable individuals as having "An increased likelihood of being wronged or of incurring additional harm." (World Medical Association 2013) For the purpose of this study, we define vulnerable individuals as those whose capacity to protect or exercise their rights is restricted due to their mental, social, economic, or ethnical status, age, or health condition. Subjects deemed vulnerable by the IRB and/or the principal investigator will not be eligible for this study.

This study involves children who have not attained the legal age for consent to treatment or procedures involved in research and are a vulnerable population. Children are a group already burdened by COVID-19 and flu and while there is no benefit to study participants, the anterior nares swabs for this study does not pose greater than a minimum risk to children.

#### 3.3 Subject Enrollment

Once informed consent is obtained, the subject will be assigned a subject ID number. The subject ID number will consist of the study site number followed by a 3-digit sequentially assigned subject number. For example, the first subject enrolled at site 01 will be assigned 01-001, with subsequent enrolled subjects assigned 01-002, 01-003, etc. The site will maintain an enrollment log that correlates the subject ID number to the subject's name.

The unique subject ID number will be written on each page of the Case Report Form (CRF) and all other documentation related to the subject. All data will be captured on the paper CRF.

#### 3.4 Baseline Data

The site will provide a narrative describing how the testing simulated a home environment. For example, whether a table and chair were provided, how subjects could sanitize their hands, positioning of the subject such that they could not observe others conducting the test, and position of the observer.

Upon confirmation of eligibility to participate in the study, the following information will be obtained:

- Age (For subjects under 14 years of age, the age of the person collecting and testing the sample will also be recorded.)
- Sex
- Race
- Ethnicity
- Educational Level (For subjects under 14 years of age, the educational level of the person performing the test will be recorded.)

- Occupation (For subjects under 14 years of age, the occupation of the person performing the test will be recorded.)
- Exposure to someone with COVID-19, and the number of days prior to the visit the exposure occurred.
- Presence or absence of respiratory symptoms: fever or chills; cough; shortness of breath; difficulty breathing; muscle or body aches, new loss of taste or smell. Subjects will be asked the date each symptom appeared.
- COVID-19 vaccine status and number of doses, manufacturer, and date of last vaccine.
- Flu vaccine status and date of vaccine, if applicable.

